## 9. Secondary Statistical Analyses

### 9.1. Secondary Efficacy Endpoint Analyses

#### 9.1.1. Overview of Planned Analyses for Secondary Efficacy Endpoints

Unless otherwise stated, analyses of secondary efficacy endpoints will be based on the intent-to-treat analysis set (ITT) and per-protocol (PPS) set.

**Table 6 Planned Overview of Secondary Efficacy Endpoint Analyses**

	Data Presentation Generated		
	Table	Figure	Listing
Incidence of recurrence or progression of SDH at 360 days after randomization: Same as Table 4 Overview of planned primary statistical analyses			
Categorical secondary endpoints: Success rate of target blood vessel embolization in DSA imaging Change in mRS score at 90 days and 360 days after randomization compared to baseline Proportion of patients with mRS score of 0 to 2 at 90 days and 360 days after randomization Proportion of patients with mRS score of 0 to 3 at 90 days and 360 days after randomization Destination for rehabilitation after discharge (going home vs rehabilitation hospital)			
Statistical description of categorical data: Number (n) and percentage of subjects in each category			
Dichotomous data analysis: - Proportion and its 95% CI - Difference in sample rate between MMA embolization and control groups, p-value and 95% CI - OR for MMA embolization and control groups with 95% CI	Y		Y
Continuous Secondary Endpoints: Changes of hematoma thickness in CT or MRI imaging at 90 days after randomization compared to baseline Changes of hematoma volume at 90 days after randomization Changes of midline shift in CT or MRI imaging at 90 days after randomization Changes of mRS score at 90 days and 360 days after randomization Quality of life evaluated with EQ-5D-5L Scale at 90 days and 360 days after randomization Total hospital stay (number of days) Re-hospitalization times Total hospitalization expenses			
Statistical description of continuous data: - Number of non-missing cases (n) - Mean (standard deviation)	Y		Y

	Data Presentation Generated		
	Table	Figure	Listing

 
- Median
 
- Min, Max
 
- Q1,Q3
 
 
Continuous data analysis:
 
 
- Estimate of mean and 95% CI for MMA embolization and control groups
 
- Difference in means and 95% CI between MMA embolization and control groups
 
- P value for difference in means between MMA embolization and control groups
 
			

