6.4 Randomization

The assignment for each subject into either the control group (no MMA embolization) or the study group (MMA embolization) will be determined by the randomization scheme. SAS (version 9.4 or updated) is used to generate the randomization list by a stratified randomization method. During screening, a unique identification number (screening number) is allocated to each subject who has provided the signed ICF. The annotation for the screening number includes a subject number and site number (e.g., the first subject in 01 site is 01001). This digital ID is allocated according to the order of entry into the study after the subject signs the ICF at the study site.

On day 0 of the trial, subjects obtain the corresponding randomization numbers and will be randomized to the study group or the control group at a ratio of 1:1.

The randomization number of subjects in all study groups is designated as #: D-ZZZ

D = representing the treatment group; expressed with Arabic numerals 1-X, where 1 represents the study group and 2 represents the control group.

ZZZ=Subject digital ID

Treatment allocation in this study is not blinded.

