Appendix 1. Study Flowchart

Study procedure	Screening period ^a	Baseline	Follow-up period			
			V0	V1	V2	V3
Visit time ^b	Day -14 to Day 0	Day 0		Discharge	Day 30	Day 90
Informed consent	X					
Demographic data	X					
Inclusion/exclusion criteria		X				
Medical history and previous medication	X					
Vital signs	X			X	X	X
Admission examination ^c	X					
CT/MRI ^d	X				X	X
DSA ^e		X				
Randomization and treatment		X				
Total hospitalization expenses			X		X	X
Efficacy endpoints					X	X
SAEs					X	
SDH-related death events					X	
Severe surgery-related complications					X	
Concomitant medication/treatment			X	X	X	X
mRS score	X				X	X
EQ-5D scale	X				X	X

^a Screening visit and baseline visit can be conducted on the same day

^b The visit time window is ± 7 days for V3, ± 14 days for V4, and ± 30 days for V5

^c Blood routine (red blood cell count, white blood cell count, platelet count, hemoglobin), coagulation (APTT, INR), hepatic and renal function (ALT, AST, BUN, Cr), electrolytes (potassium, sodium, chlorine), random blood glucose; urine HCG test is required for female of child-bearing potential

^d CT is mandatory and MRI is optional. The doctor should decide whether MRI is necessary based on the condition of the patient

^e This item is conducted only in MMA embolization group

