### 8.2.2. Analysis Methods

- The primary analysis will compare groups using the CMH chi-square test (the stratification factor is whether or not to perform trepanation/drainage was performed), summarize the 90-day recurrence (trepanation/drainage group) / progression rate (non-surgical group) for the MMA embolization group and the control group using the two-sided 95% CI (Clopper-Pearson method) and summarize the two-sided 95% CI for the difference in recurrence or progression rates between the two groups using the Miettinen-Nurminen method.
- Sensitivity analyses will use generalized linear mixed-effects model to calculate ORs and their 95% CIs for the comparison of recurrence or progression rates between the two arms, with group as fixed effect, site as random effect. Results of multivariable analysis will also be

presented, including treatment group, sex, age, surgical treatment strata (trepanation/drainage vs. no trepanation/drainage), any usage of antiplatelet or anticoagulant therapy, hematoma volume of baseline CT as covariates.

Enter Analysis Methods and Results Presentation

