### 9.1.2.2. Statistical Analysis Methods

- 360 days recurrence or progression of SDH after randomization will be analyzed in the same way as the primary endpoint (Section8.2.2)
- Ordinal logistic regression will be used for intergroup comparison of mRS scale scores at 90 and 360 days after randomization, with treatment group, sex, age, surgical treatment strata (trepanation/drainage vs. no trepanation/drainage), any usage of antiplatelet or anticoagulant therapy within one month before randomization(yes vs no), hematoma volume of baseline CT as covariates.
- Other categorical secondary endpoints will be analyzed in the same way as the primary endpoint **(Error! Reference source not found.Error! Reference source not found.Section)**

- The linear mixed effects model approach will be used to estimate the mean estimate (95% CI) and the mean estimate (95% CI) of the differences between groups as well as the P values of the differences between groups for the change in maximum hematoma thickness at 90 days after randomization compared to baseline and the change in hematoma volume at 90 days after randomization compared to baseline; Treatment group variables, sex, age, surgical treatment strata (trepanation/drainage vs. no trepanation/drainage), any usage of antiplatelet or anticoagulant therapy within one month before randomization(yes vs no), hematoma volume of baseline CT , visit variables, and visit by treatment group variable interactions will be included in the model and site as the random effect.
- For other continuous secondary endpoints, T tests will be used to compare groups, and 95% confidence intervals for the difference in means between groups will be calculated using normal approximation.

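### Embolization success is assigned a between-arm difference, p-value and odds ratio, although control patients are not embolized

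*SAP*

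**What the plan says.** SAP Table 6 opens its categorical block with "Success rate of target blood vessel embolization in DSA imaging". Among the analysis rows for that block are "Difference in sample rate between MMA embolization and control groups, p-value and 95% CI" and "OR for MMA embolization and control groups with 95% CI".

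SAP Section 9.1.2.2 gives separate methods to 360-day recurrence or progression and to the mRS scores, and then states: "Other categorical secondary endpoints will be analyzed in the same way as the primary endpoint". For the primary endpoint, SAP Section 8.2.2 says: "The primary analysis will compare groups using the CMH chi-square test". It adds a Clopper-Pearson interval per arm, a Miettinen-Nurminen interval for the difference, and mixed-model odds ratios as sensitivity analysis. SAP Section 9.1.1 says that, by default, "analyses of secondary efficacy endpoints will be based on the intent-to-treat analysis set (ITT) and per-protocol (PPS) set".

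Protocol Section 7.3.2 also includes embolization success in its secondary list and prescribes inter-group tests for that list.

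On who can have the outcome, Protocol Section 6.4 and the assignment row of SAP Section 1.3 define control as no MMA embolization. The note on DSA in Protocol Appendix 1 reads: "This item is conducted only in MMA embolization group". SAP Appendix 1 carries the same restriction. Protocol Section 5.3 defines success as selective occlusion of the MMA trunk, or of both its frontal and parietal branches.

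**The concern.** A technical success rate exists only where the procedure was attempted. Comparing it between an arm that is assigned the procedure and one that is not tests whether embolization was assigned, which is already known from the randomization list.

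Followed literally, the SAP leads either to a programming failure or to a p-value that assignment makes significant in practice. SAP Section 1.2 places this endpoint under the objective of validating the efficacy of MMA embolization, so that p-value would appear among the secondary efficacy results. Meanwhile the useful quantity, technical success with its precision, has no stated denominator.

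**Working it through.** **Inputs.** Total sample size 722, allocation 1:1, rates 5% and 12%, two-sided alpha 0.05, power 90%, loss 8% (Protocol 7.1.3; SAP Section 3). Control means no MMA embolization (Protocol 6.4). No success rate is given anywhere, so the rates below are assumptions.

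**Arm size.** The plan's own figure reproduces with the pooled-variance formula:

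n = [1.96·√(2 × 0.085 × 0.915) + 1.2816·√(0.12 × 0.88 + 0.05 × 0.95)]² / 0.07² ≈ 331.5, so 332 per arm.

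332 / 0.92 = 360.9, so 361 per arm and 722 in total. The sample size is not in dispute; it only supplies the arm size.

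**Reading A: controls have no value.** There is no comparator, so no difference, CMH statistic or odds ratio exists. SAP Section 9.1.2.1 also carries over the derivations of Section 8.2.1, which impute when more than 5% of data are missing. Here 361/722 = 50% would be missing. The sample code in SAP Appendix 3 imputes separately by treatment group, and the control group would have no observed outcome to impute from.

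**Reading B: controls stay in the denominator.** The proportion rule in SAP Appendix 2 keeps missing observations in the denominator, which gives controls 0/361. With a successes among n = 361 in the embolization arm and 0 among 361 controls:

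- difference = a/361 − 0, which is the embolization-arm rate itself;
- sample odds ratio = (a × 361) / [(361 − a) × 0], which is infinite; the mixed-model odds ratio is not estimable for the same reason;
- uncorrected, unstratified chi-square = 2n·a / (2n − a) = 722a / (722 − a).

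| Successes of 361 | Rate | Chi-square | p |
|---|---|---|---|
| 4 | 1.1% | 722 × 4 / 718 = 4.02 | 0.045 |
| 289 (assumed) | 80% | 722 × 289 / 433 = 482 | about 10⁻¹⁰⁶ |
| 325 (assumed) | 90% | 722 × 325 / 397 = 591 | about 10⁻¹³⁰ |
| 361 (assumed) | 100% | 722 × 361 / 361 = 722 | about 10⁻¹⁵⁸ |

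With 3 successes the statistic is 722 × 3 / 719 = 3.01, below 3.84, so 4 is the smallest count that crosses the 5% level. A procedure that failed in 357 of 361 patients would still be reported as significantly better than control.

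**What a one-arm report would give.** Clopper-Pearson 95% intervals with 361 patients, at assumed rates:

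| Successes | Rate | 95% CI |
|---|---|---|
| 289/361 | 80% | 75.6–84.1% |
| 325/361 | 90% | 86.5–92.9% |
| 343/361 | 95% | 92.2–97.0% |
| 354/361 | 98% | 96.0–99.2% |

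**The case against.** Table 6 is an overview, and not every row can apply to every endpoint in its block. Change in mRS score sits in the same block although it is not dichotomous, and Section 9.1.2.2 gives it ordinal regression. The block also has descriptive rows (counts, and a proportion with its interval) that supply most of what is needed. This weakens an argument from table layout alone. It does not answer the catch-all sentence in Section 9.1.2.2, which covers embolization success because no other method is given for it.

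The 0/361 coding is nowhere stated. Controls could be treated as not applicable, a category that Protocol Section 11.3 separates from not available, and a sensible programmer would probably leave the control column blank. That is fair: Reading B depends on a coding choice. But Reading A gives no computable contrast either, and a blank column, though sensible, would depart from the SAP as written.

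Protocol Section 6.5 lists DSA among the examinations before randomization without naming an arm, and off-protocol embolization of a control is not ruled out. The first point conflicts with both flowcharts and must be reconciled. Neither rescues the test: a diagnostic angiogram cannot show a successful embolization, and with crossovers the contrast would be driven by crossover.

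Finally, the consequence is small. The only stated hypothesis concerns 90-day recurrence or progression, no testing hierarchy uses this p-value, and an informed reader would discount it. That stands and limits the weight of the point.

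**Conclusion.** The concern holds. The SAP prescribes a between-arm analysis for an outcome that control patients cannot have, and nothing in either document exempts the endpoint or restricts it to one arm. This is a stated analysis that is wrong as written, not merely a missing detail.

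The 0/361 results depend on keeping controls in the denominator and on no control being embolized. The chi-squares of 482–722 also rest on assumed success rates of 80–100%. The conclusion does not depend on those rates, because under either reading the contrast says nothing about treatment effect. The impact is confined to one technical secondary endpoint. It should be corrected, but it does not threaten the trial's main result.

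**What to change.** - In SAP Section 9.1.2.2, exclude embolization success from the rule for other categorical endpoints and state that it is descriptive and limited to the embolization arm. State also that the imputation rule of Section 8.2.1 does not apply to it.
- In SAP Table 6, move it out of the block with the difference, p-value and odds-ratio rows. Report n/N, percentage and Clopper-Pearson 95% interval, with no control column.
- Name the denominator. All patients allocated to embolization matches the ITT set; all patients in whom it was attempted can be added as a second line.
- Reconcile the DSA entry in Protocol Section 6.5 with the flowchart notes in both documents.

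The cost is a few lines of SAP text and one table shell. No new data are needed, and the sample size and primary analysis do not change.

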## 9.1.2. Specifications of Secondary Efficacy Endpoint Analyses

### 9.1.2.1. Definitions and Derivations

- Change from 90 days/360 days post study treatment will be calculated as 90 days/360 days measurement – baseline measurement
- Total days in hospital = Date of discharge - Date of hospitalization + 1 (Hospital information page)
- Other definitions and derivations are the same as in Section 8 .2.1

### 9.1.2.2. Statistical Analysis Methods

- 360 days recurrence or progression of SDH after randomization will be analyzed in the same way as the primary endpoint (Section8.2.2)
- Ordinal logistic regression will be used for intergroup comparison of mRS scale scores at 90 and 360 days after randomization, with treatment group, sex, age, surgical treatment strata (trepanation/drainage vs. no trepanation/drainage), any usage of antiplatelet or anticoagulant therapy within one month before randomization(yes vs no), hematoma volume of baseline CT as covariates.
- Other categorical secondary endpoints will be analyzed in the same way as the primary endpoint **(Error! Reference source not found.Error! Reference source not found.Section)**

- The linear mixed effects model approach will be used to estimate the mean estimate (95% CI) and the mean estimate (95% CI) of the differences between groups as well as the P values of the differences between groups for the change in maximum hematoma thickness at 90 days after randomization compared to baseline and the change in hematoma volume at 90 days after randomization compared to baseline; Treatment group variables, sex, age, surgical treatment strata (trepanation/drainage vs. no trepanation/drainage), any usage of antiplatelet or anticoagulant therapy within one month before randomization(yes vs no), hematoma volume of baseline CT , visit variables, and visit by treatment group variable interactions will be included in the model and site as the random effect.
- For other continuous secondary endpoints, T tests will be used to compare groups, and 95% confidence intervals for the difference in means between groups will be calculated using normal approximation.

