
- Symptomatic SDH recurrence and progression rate within 90 days post-procedure

Symptomatic SDH recurrence refers to the maximum thickness of hematoma exceeding 10 mm combined with neurological symptoms, or the patient requires re-operation (surgery group);

Symptomatic SDH progression refers to the maximum thickness of hematoma increasing by more than 3 mm compared with baseline, or the patient requires operation (drug therapy group).

Secondary efficacy endpoints:

- Symptomatic SDH recurrence and progression rate at 360 days post-procedure
- Success rate of target vessel embolization (MMA trunk and branch vessels) on digital subtraction angiography (DSA) imaging
- Change in hematoma thickness on computed tomography (CT)/magnetic resonance imaging (MRI) at 90 days post-procedure
- Change in hematoma volume at 90 days post-procedure
- Change in midline shift on CT/MRI imaging at 90 days post-procedure
- Change in mRS score at 90 days and 360 days post-procedure
- Proportion of patients with mRS score ≤ 2 at 90 days and 360 days post-procedure
- Proportion of patients with mRS score ≤ 3 at 90 days and 360 days post-procedure
- Quality of life evaluated with EQ-5D Scale at 90 days and 360 days post-procedure

- Total hospital length of stay, number of re-hospitalizations, discharge location (home vs. rehabilitation hospital), and total hospitalization expenses

The safety endpoints in this study include:

- Serious adverse events (SAEs) within 90 days and 360 days;
- SDH-related mortality within 90 days and 360 days;
- Severe surgery-related complications within 30 days post-procedure (including surgery and embolization)
 - Symptomatic intracranial hemorrhage
 - Surgery-related intracranial hemorrhage
 - Surgery-related neurological deficits
 - Surgery-related central nervous system infection
 - Surgery-related arterial dissection, vascular wall injury, and vascular rupture and perforation
 - Surgery-related ischemia
 - Retroperitoneal/wrist hematoma
 - Neuropathy at the puncture site
 - Contrast allergy or contrast encephalopathy

Note: Follow-up time at 30 days, 90 days, and 360 days post-procedure will be calculated based on the day of randomization in this study. Relevant endpoint events and safety events will be collected at these follow ups.

3. Study Design

[figure not shown]

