
 
To validate the safety of MMA embolization with liquid embolic materials
 
	
 
Serious Adverse Events (SAEs) within 90 days and 360 days
 
Death within 90 days and 360 days
 
Severe surgery-related complications within 30 days after surgery (including trepanation/drainage and MMA embolization): 
 
Symptomatic intracranial hemorrhage
 
Surgery-related intracranial hemorrhage
 
Surgery-related neurological deficits
 
Surgery-related central nervous system infection
 
Surgery-related arterial dissection, vascular wall injury and vascular rupture and perforation
 
Surgery-related ischemia
 
Access site hematoma
 
Neuropathy at the puncture site
 
Contrast allergy or contrast encephalopathy
 
 
 

 
To validate the reduction of residual hematoma at 90 days after randomization in patients
 
	
 
Changes of hematoma thickness on CT/MRI imaging at 90 days after randomization
 

Study objectives	Study Endpoints
undergoing MMA embolization	
 
Changes of hematoma volume at 90 days after randomization
 
Changes of midline shift in CT/MRI imaging at 90 days after randomization
 

 
To validate the improvement in clinical outcome (mRS score) at 90 days and 360 days after randomization in patients undergoing MMA embolization
 
	
 
Changes of Modified Rankin Scale (mRS) score at 90 days and 360 days after randomization
 
Proportion of patients with mRS score of 0 to 2 at 90 days and 360 days after randomization
 
Proportion of patients with mRS score of 0 to 3 at 90 days and 360 days after randomization
 

 
To validate the improvement in health status (EQ-5D-5L scale) at 90 days and 360 days after randomization in patients undergoing MMA embolization
 
	
 
Quality of life evaluated with EQ-5D-5L Scale at 90 days and 360 days after randomization
 

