### 9.1.2.3. Model Specifications

Statistical analysis of binary categorical variables
Endpoints and parameters

 
● Endpoint: Change of mRS scale score at 90 and 360 days after randomization compared to baseline
 
● Parameters: 
 
– Ordinal OR and 95% CI
 
 
 

Input Variables

 
● AVAL: response variable
 
● TRTAN: groups
 
● SITEID: subject site number
 
● COUNT: number of subjects per level per group
 
● COVARIATES: adjusted Variables
 

SAS Code Sample

Logistic Regression Example Code:
 <pre>proc glimmix data=adeff descending;   class siteid trtan;   model aval/ count = trtan covariates / solution;</pre>

random intercept / subject= siteid; run;
Presentation of Results

 
The OR and 95% CI for the ratio can be obtained from Odds Ratio Estimates.
 

Statistical analysis of continuous variables
Endpoints and parameters

 
Endpoint: 
 
Changes of hematoma thickness in CT or MRI imaging at 90 days after randomization compared to baseline
 
Changes of hematoma volume at 90 days after randomization compared to baseline
 
Changes of midline shift in CT or MRI imaging at 90 days after randomization compared to baseline
 
Quality of life evaluated with EQ-5D-5L Scale at 90 days and 360 days after randomization compared to baseline
 
Total hospital stay (number of days)
 
Re-hospitalization times
 
Total hospitalization expenses
 
 
 
Parameters: 
 
Mean and 95% CI
 
Difference in means and 95% CI with P-value
 
 
 

Input Variables

 
AVAL: response variable
 
TRTAN: group
 
SITEID: subject site number
 
AVISITN: visit variables
 
COVARIATES: adjusted variables
 

SAS Code Sample

Linear Mixed Effects Model Method Example Code:
 <pre>proc mixed data = adeff; class trtan siteid avisitn; model aval = trtan covariates avisitn avisitn avisitn trtan/solution ddfm = kr; random siteid /type = cs; lsmeans trtanavisitn/diff cl alpha = 0.05 e; ods output lsmeans = lsmeans diff = diff; run;</pre>

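### Thickness change, mRS, midline shift and EQ-5D are analysed without adjusting for their own baseline value, and the SAP conflicts on the mRS and EQ-5D responses; the cost is precision or power on secondary endpoints only

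*SAP*

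**What the plan says.** **Covariates.** SAP 9.1.2.2 gives a full list for thickness change and volume change: treatment, sex, age, trepanation stratum, antithrombotic use, baseline hematoma volume, visit and visit-by-treatment, with site random. Volume therefore has its own baseline in the model and thickness does not. For mRS, "Ordinal logistic regression will be used for intergroup comparison of mRS scale scores at 90 and 360 days after randomization", with the same baseline covariates; baseline mRS is not among them. Midline shift and EQ-5D come under the remainder rule: "For other continuous secondary endpoints, T tests will be used to compare groups". The t-test code in 9.1.2.3 has only treatment and response. (SAP Table 1 also allows a Mann-Whitney test here, equally unadjusted.)

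**Availability.** Baseline mRS and EQ-5D are assessed under Protocol 6.5. Baseline thickness and midline shift distance are in SAP Table 3.

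**mRS response.** It is the score in 9.1.2.2. In 9.1.2.3 the model specification reads "Endpoint: Change of mRS scale score at 90 and 360 days after randomization compared to baseline". SAP 1.2 names "Changes of Modified Rankin Scale (mRS) score at 90 days and 360 days after randomization" and Protocol sections 2 and 7.3.2 name "Change in mRS score at 90 days and 360 days post-procedure". SAP Table 6 lists change twice, as categorical ("Change in mRS score at 90 days and 360 days after randomization compared to baseline") and as continuous ("Changes of mRS score at 90 days and 360 days after randomization").

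**EQ-5D response.** SAP 1.2 and Table 6 give the visit value ("Quality of life evaluated with EQ-5D-5L Scale at 90 days and 360 days after randomization"). Only 9.1.2.3 sets it against baseline.

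**Related differences.** The visit terms of 9.1.2.2 and 9.1.2.3 are absent from the same model in Table 1. The multivariable model for the primary endpoint includes baseline thickness and baseline mRS in Table 1. In 8.2.2 it has neither, and uses the stratum, antithrombotic use and baseline volume instead.

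**The concern.** A follow-up measurement usually correlates with its own baseline, and adjusting for that baseline removes variance that a t-test leaves in. The SAP does this for volume but not for the parallel endpoints. It considers baseline mRS and thickness informative enough for the imputation model in 8.2.1, yet leaves them out in 9.1.2.2. What is at stake is precision for thickness, midline shift and EQ-5D, and power for mRS.

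The conflicting responses are a separate problem. For mRS, an ordinal model of the score, an ordinal model of change, and a t-test on change can each be read from the text. SAP 1.1 says Table 1 summarizes all analysis changes, but Table 1 does not mention the ordinal mRS model, so it cannot settle the question. For EQ-5D, two analyses are open.

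**Working it through.** **1. The plan's own figure.** Inputs from Protocol 7.1.3: 12% against 5%, two-sided 5%, power 90%, 8% loss. The pooled-variance formula gives 331.5, so 332 per arm and 664 in total; 664 / 0.92 = 721.7, so 722. The stated size reproduces and does not depend on the endpoints discussed here.

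**2. Assumed inputs.** The documents give no SD or correlation for these endpoints. Let r be the baseline to follow-up correlation (0.3, 0.5, 0.7) and k the follow-up SD divided by the baseline SD (0.75, 1, 1.5).

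**3. Change-score t-test against ANCOVA** (midline shift; EQ-5D if read as change). In baseline-variance units the change has variance 1 + k² − 2rk and ANCOVA leaves k²(1 − r²). Extra patients = (1 + k² − 2rk) / [k²(1 − r²)] − 1.

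| k | r = 0.3 | r = 0.5 | r = 0.7 |
|---|---|---|---|
| 0.75 | 117% | 93% | 79% |
| 1 | 54% | 33% | 18% |
| 1.5 | 15% | 4% | 0.2% |

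Example at k = 1, r = 0.5: 1.0 / 0.75 = 1.33. With 332 evaluable per arm, k = 1 and an assumed difference of 0.2 SD, power is 59 / 73 / 91% for the t-test on change and 77 / 85 / 95% for ANCOVA at r = 0.3 / 0.5 / 0.7.

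**4. Visit-value t-test against ANCOVA** (EQ-5D as in SAP 1.2 and Table 6). Extra patients = 1/(1 − r²) − 1 = 10 / 33 / 96%.

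**5. Thickness.** Baseline volume and the other planned covariates act as a partial proxy. Let R² be the share of baseline thickness that they explain, and assume they affect day-90 thickness only through it. Extra patients = (1 − rk)²(1 − R²) / [k²(1 − r²)]. Entries run from r = 0.3 to r = 0.7.

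| k | R² = 0.25 | R² = 0.80 |
|---|---|---|
| 0.75 | 88% to 59% | 24% to 16% |
| 1 | 40% to 13% | 11% to 4% |
| 1.5 | 11% to 0.2% | 3% to 0% |

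**6. mRS.** Proportional-odds fits under several assumed distributions. In set A: 664 patients, conditional log OR 0.4 (OR 1.49), baseline mRS 0-4 shares of 5/35/30/20/10%, outcome levels 0-6, and one composite for the other covariates (log OR 0.6 per SD, correlation 0.3 with latent baseline mRS). Sets B to D use other assumed outcome distributions. Power levels depend on these inputs, so only gaps within a row should be read.

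| Set (baseline-outcome Spearman) | Score | Score + baseline | Change | Change + baseline |
|---|---|---|---|---|
| A (0.36) | 74% | 78% | 61% | – |
| A (0.51) | 64% | 76% | 66% | – |
| B (0.39) | 76% | 81% | 75% | – |
| B (0.54) | 72% | 82% | 77% | – |
| C (about 0.35) | – | 82% | – | 80% |
| C (about 0.50) | – | 78% | – | 77% |
| D (two settings) | 68%, 63% | 79%, 81% | – | about 78% |

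For the score, adding baseline mRS gains 4 points (A, 0.36) to 18 points (D, second setting). In set A the standard error hardly moves (0.145 without baseline; 0.147 and 0.150 with it). The odds ratio without baseline is 1.46 or 1.40 against 1.49, so the loss appears as a smaller estimate and not as a wider interval.

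**7. Value and change in a linear model.** If Y − X = a + τT + bX, then Y = a + τT + (b + 1)X. The treatment effect τ is the same. This identity does not carry over to the ordinal mRS model.

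**8. Validity.** In simulation at r = 0.2, 0.5 and 0.7, type I error was 0.044 to 0.048 for the t-test on value, the t-test on change, and ANCOVA.

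**The case against.** The strongest reply is that covariate choice for secondary endpoints is a matter of efficiency. Change scores already use baseline by subtraction, thickness is partly adjusted through volume, and every loss above rests on assumed r, k and R². This stands as a limit on severity. It does not remove the gain, which is nearly free, or the conflicting responses.

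Three stronger readings are tempting, and the documents do not support them.

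- *The mRS endpoint must become the score.* The protocol names change. With baseline mRS in the model, change has about the same power as the score (80% against 82%, and 77% against 78%, in set C), so replacing the endpoint is not needed for power.
- *The visit terms are redundant.* CT/MRI is scheduled at day 90 and day 360 (SAP Appendix 1) and read centrally at both (Protocol 11.6), and SAP 9.1.2.3 extracts same-visit contrasts. A two-visit model is a reasonable reading. Table 1 and 9.1.2.2 need reconciling, and the documents do not show which is intended.
- *One reduced linear model should serve all endpoints.* That would drop planned covariates (sex, age, antithrombotic use) from the hematoma models. Volume would gain nothing, and the assumption in step 5 makes the loss for thickness look costless by construction.

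It is also fair to say that the mRS power levels are illustrative. The outcome shares are assumed, and Protocol Appendix 3 as supplied lists levels 0-5 where set A uses 0-6. Finally, the EQ-5D form in Protocol Appendix 2 has five items and a 0-100 scale, and the SAP should name the measure analysed before its baseline is defined.

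**Conclusion.** The concern holds for secondary endpoints, at minor to moderate severity. Own-baseline adjustment is missing for thickness, mRS, midline shift and EQ-5D although the data are collected. Under the assumed ranges the cost is 0-117% more patients for a change-score t-test, 10-96% for a visit-value t-test, 0-88% for thickness, and roughly 4-18 points of power for mRS. The low ends are real possibilities: with k = 1.5 and r = 0.7 nothing material is lost on change scores.

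A reader might infer that the planned comparisons are biased or that the trial's main result is at risk. Neither follows. Under randomization the tests are unbiased and keep their type I error, and neither the primary endpoint nor the 722 is touched. The smaller mRS odds ratio without baseline is partly a different (less conditional) quantity, so it should not be called bias.

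The mRS and EQ-5D conflicts are matters of text and need no assumption. As written, more than one analysis is open for each.

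**What to change.** 1. Keep the planned covariates. Add baseline thickness to the thickness model and baseline mRS to the ordinal mRS model. Leave the volume model's covariates as they are.
2. Replace the t-test for midline shift and EQ-5D with a linear model containing treatment, the endpoint's own baseline, the pre-randomization trepanation stratum, and site as random effect. For EQ-5D, value and change then give the same treatment contrast.
3. Fix one mRS response before the analysis, with baseline mRS as covariate, and make SAP 1.2, Table 6, 9.1.2.2 and 9.1.2.3 agree. The protocol's change endpoint can be kept with little or no loss of power; if the score is chosen, record it.
4. Reconcile Table 1 with 9.1.2.2 and 9.1.2.3 on the visit terms: either a day-90 model without them, or a stated day-90 and day-360 model from which the day-90 contrast is taken.
5. Record every departure from Protocol 7.3.2 in Table 1, including the replaced t-tests, and reconcile the multivariable covariate sets in Table 1 and 8.2.2.

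Cost: a little more SAP text and code, several Table 1 entries and no new data. The mRS odds ratio becomes conditional on baseline mRS and should be described that way.
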